#### 4.7 Dose Regimen and Treatment Period Rationale

The dose and dose schedule for the Phase 2 study is 100 µg/kg, weekly for a duration of 5 weeks (6 doses). This dose was selected based on nonclinical pharmacology and toxicology information and the safety and exploratory efficacy results of the Phase 1/2a FIH study.

In murine models of GvHD, doses as low as 2 µg/mouse (approximately 100 µg/kg) prolonged the survival of mice. Additional studies showed prolongation of survival in these murine models was noted over a dose range of 0.1 to 10 µg/kg. As there was no sign of decreasing efficacy with dose, these mouse models suggested a dose of 100 µg/kg was toward the top of a wide range of effective doses.

In 2-week GLP toxicity studies of RGI-2001 in the mouse and monkey, the NOAEL was the highest dose tested in each species, 50 and 20 mg/kg, respectively. The HED of these doses are 44-fold and 65-fold higher than the planned dose of 100 µg/kg in study RGI-2001-003. Exposure of mice and monkeys at the NOAEL, based AUC0-t was very large, 2,155,000 ng\*h/mL and 12,950,000 ng\*h/mL, respectively. These exposures are over 10,000-fold higher than the human AUC0-t associated with a dose of 100 µg/kg (133 ng\*h/mL, n = 15, study RGI-2001-002, Part 2).

Longer term toxicity of the active agent (RGI-7000) given by daily IV injection has been evaluated in GLP studies in rats (50, 100, 200, and 400 µg/kg/day for 26 weeks) and monkeys (30, 60, 200, and 600 µg/kg/day for 15 weeks), with a toxicity pattern similar to that of RGI-2001 suggesting there is no change in the toxicity of the active agent of RGI-2001 with longer duration of treatment.

Further support for the selection of 100 µg/kg comes from the clinical safety seen in study RGI-2001-002, in which RGI-2001 was safe and well tolerated up to 100 µg/kg administered as a single intravenous infusion for subjects who received allogeneic transplantation. There were no notable adverse effects across a variety of conditioning regimens and GvHD prophylaxis. Possible efficacy was observed in subjects during Part 1 (dose escalation) of the study but the differences between doses were not clear because of the small sample sizes. In Part 2 (dose expansion), both doses at 1.0 µg/kg and 100 µg/kg dose level showed some signal of effect and

there was no increase toxicity at the highest dose evaluated. There were no trends in toxicity with dose escalation across all the cohorts. Therefore, RGI 2001 at 100 ug/kg was selected to further evaluated for repeat dosing for the clinical development program.

Potential signals of efficacy from a single dose of RGI-2001 in study RGI-2001-002 support further testing of repeated (weekly) doses of RGI-2001 in this study. The weekly interval was selected to extend the exposure seen in the single dose clinical trial RGI-2001-002, while minimizing subject inconvenience with clinic visits.

**5 STUDY OBJECTIVES AND ENDPOINTS**

Objectives	Endpoints
Primary	

 
To assess the potential efficacy of RGI-2001 in addition to standard of care (SOC) vs SOC for the prevention of aGvHD
 
To characterize the safety and tolerability of 6-weekly IV infusions of RGI-2001 in subjects following alloHSCT
 
	
 
Efficacy: Grades II-IV aGvHD by Day 100 according to the Modified Keystone Criteria (Przepiorka 1995)
 
Safety: Incidence, nature, and severity of treatment-emergent AEs, SAEs, laboratory test values, vital sign measures, and graft failure
 

Secondary	

 
To assess the potential efficacy of RGI-2001 in addition to SOC vs SOC for the prevention of chronic GvHD (cGvHD) according to the secondary endpoints listed
 
To assess the survival of subjects who received RGI-2001 in addition to SOC vs SOC
 
To evaluate the pharmacodynamics effects of weekly dosing of RGI-2001
 
	
 
Grades II-IV aGvHD by Day 180 according to the Modified Keystone Criteria
 
Total and moderate-severe cGvHD at 6 months and 1 year according to 2014 NIH criteria
 
Non-relapse mortality (NRM) rates at Day 100, 6 months and 1 year
 
Disease-free survival (DFS) at 6 months and 1 year
 
GvHD-free, relapse free survival (GRFS)a at 6 months and 1 year
 
Overall survival (OS) at 6 months and 1 year
 
Change from baseline in the percentage of CD4+CD25+CD45RA+ CD127-LO T cells (naive Tregs) on Days 14, 28, 42, 60, 100, 180
 

 
[REDACTED]
 
	
 
[REDACTED]
 

Objectives	Endpoints
	

• [REDACTED]

• [REDACTED]

a A GRFS event includes grade III-IV acute GVHD, chronic GvHD requiring systemic immunosuppressive treatment, disease relapse or progression, or death by any cause.

## 6 STUDY DESIGN

[figure not shown]
This is an open-label, multi-center, single-arm study to evaluate six weekly doses of RGI-2001 in combination with SOC treatment for the prevention of aGvHD in subjects following alloHSCT. The study will include a Safety Run-in Phase of up to 6 subjects to assess the safety and tolerability of 6 weekly doses of RGI-2001. If the safety profile in this run-in is deemed acceptable (see [Section 6.1](#)), an Expansion Phase in which the potential efficacy of 6 weekly doses of RGI-2001 in addition to SOC for GvHD prophylaxis will be assessed. Comparison will be made to a contemporaneous control group of subjects from the CIBMTR database in which SOC GvHD prophylaxis was administered (details in [Section 11](#)).

All subjects will be assessed for suitability of alloHSCT based on institutional practice, using either a matched-related donor (MRD) or unrelated donor (URD), and will be enrolled after meeting inclusion/exclusion criteria for this study. Preparatory regimens will be based on institutional practice for the disease subtype. Either bone marrow or peripheral stem cell grafts mobilized with G-CSF will be used. GvHD prophylaxis must consist of a calcineurin inhibitor (tacrolimus or cyclosporine) and a second agent (methotrexate or mycophenolate mofetil).

All subjects will be assessed for GvHD as per institutional practices but at minimum Day +100, +180 and 1-year post alloHSCT. Assessment of cGvHD will likewise occur at regular intervals as per institutional guidelines. Similar to the methodology employed by CIBMTR for the control subjects, cumulative data will be captured at regular intervals as outlined in the Schedule of Assessments (SoA).

- Safety will be assessed with periodic vital signs, physical exams, laboratory assessments and by reporting of AEs.
- Disease status will be assessed via regular laboratory and bone marrow assessments.

The study design is presented in [Figure 1](#).

**Figure 1 Study Design Schema**

## 6.1 Safety Run-in Phase

A Safety Run-in Phase will be used to assess the safety profile and tolerability of repeat doses of RGI-2001 prior to the Expansion Phase. This portion of the study will be conducted at a limited number of sites.

Subjects will receive open-label RGI-2001 at a dose of 100µg /kg, via 30-minute intravenous (IV) infusion on a weekly basis for 6 doses in addition to a SOC GvHD prophylactic regimen. The first dose will be administered on Day 0 at approximately 30 minutes and no later than 1 hour after HSCT infusion (see [Section 8.6](#) on Dose Administration). Subsequent doses will be administered weekly, on Days 7, 14, 21, 28 and 35.

Up to two cohorts of 3 subjects each will be enrolled to the Safety Run-in Phase. Initially, 3 subjects will be enrolled, treated and assessed for dose-limiting toxicities (as defined below in [Section 6.1.1](#)) through Day 30 (DLT window). A safety review committee (SRC) will examine all relevant safety data after the 3rd subject has reached Day 30. As a rough guide, a DLT rate on the order of 20% or less would be considered as acceptable. Therefore, if 0 subjects are reported

to have a DLT among the first 3 subjects, consideration will be given to enrolling up to 3 additional subjects. However, this decision will not be made solely on the observed occurrence (or lack of) DLTs; rather the SRC will consider the totality of the safety data before arriving at a definitive conclusion regarding enrollment of additional subjects at the dose of 100 µg /kg. If within the first 3 subjects, 1 or more DLTs are observed, then consideration will be given to use of an alternative dose and/or dosing schedule, with the ultimate decision being made by the SRC. If an alternate dose and/or schedule is used, the same process as described above will be used. If the additional 3 subjects (beyond the initial 3) are allowed to enroll at the dose of 100 µg /kg or a lower dose and/or alternative schedule, safety data after the 6th subject has completed all 6 doses, as well as initial efficacy, PK and PD data will be evaluated in coming to a recommendation regarding proceeding to the Expansion Phase, with this recommendation made by the SRC. Once the study extends to the Expansion Phase, enrollment will be open to all sites (Figure 2).

### 6.1.1 Definition of Dose-limiting Toxicities

[figure not shown]
All subjects are expected to experience hematologic toxicity as part of the myeloablative alloHSCT procedure. Therefore, hematologic toxicities (e.g., leukopenia and thrombocytopenia) will not be useful measures of drug-induced toxicity, and DLTs are defined by non-hematologic toxicities.

The following DLT criteria apply to the Safety Run-in Phase of the study. A DLT is defined as any treatment-related AE that is not attributable to an extraneous cause (i.e., disease progression, preparatory regimen or HSCT infusion) and also excludes any signs and symptoms of GvHD. DLT is an adverse event occurring in the period of 30 days after the first dose of RGI-2001 administration, and meeting at least one of the following NCI CTC (Version 5.0) criteria:

- Grade 3+ infusion-related/cytokine release reactions
- Graft failure (as defined in Section 9.4.1.)
- Any Grade 4-5 non-hematological AE
- Delay in dosing by > 2 weeks due to treatment-related AE that is not attributable to an extraneous cause as defined above

Subjects who do not complete the DLT window for reasons other than toxicity may be replaced. Similarly, if a subject receives ≤ 50% of planned doses of RGI-2001 for reasons other than toxicity considered related to RGI-2001, this subject may be replaced.

**Figure 2 DLT Schema**

## 6.2 Expansion Phase

Once a dose/schedule is determined by the SRC to have an acceptable safety/PK profile, enrollment will continue in the Phase 2 Expansion Phase and be extended to all sites.

Accrual is targeted at 50 subjects who receive the dose deemed as acceptable from the Safety Run-in Phase (44 in the Expansion Phase, 6 from the Safety Run-in Phase at the dose used in expansion). All subjects in the Expansion Phase who receive at least one dose will be considered in all efficacy and safety analyses.

Subjects will receive open-label RGI-2001 at a dose of 100µg/kg (unless an alternative dose and/or schedule is chosen by SRC), via 30-minute intravenous (IV) infusion on a weekly basis for 6 doses (or an alternative dose/schedule as determined in the run-in phase) in addition to a SOC GvHD prophylactic regimen. The first dose will be administered on Day 0 at approximately 30 minutes and no later than 1 hour after HSCT infusion. Subsequent doses will be administered weekly, on Days 7, 14, 21, 28 and 35.

## 6.3 Control Group

A non-randomized, contemporary control group from the CIBMTR database will be derived for comparison. Control subjects will be chosen so as to meet all eligibility requirements for the clinical trial, have received a transplant in the same time window as the study subjects, and have been transplanted in a center that participates in this study. Consent will be obtained via the CIBMTR to participate in this study ([Section 11](#)).

## 6.4 Safety Review Committee

As noted above, a safety review committee will be used in this study. The SRC will serve 3 primary roles: 1) assessment of DLTs, other safety measures, and PK/PD in the initial 3 subjects to determine whether dose and schedule appropriate to enroll another 3 subjects 2) assessment of safety and PK/PD data to determine suitability to proceed to dose expansion 3) ongoing monitoring of both safety and aggregated efficacy data. The SRC will develop and follow a data and Safety Monitoring Plan and charter.

The SRC will be composed of, at a minimum the Sponsor or designee members including the Medical Monitor, Statistician, Safety Scientist, and the Lead Principal Investigator (PI). SRC meetings will occur in accordance with the SRC charter.

Depending on the results of safety reviews, the SRC may provide recommendations on the future continuation of the study and other relevant steps, including prophylactic pre-medications in all or some current and future subjects.

## 6.5 Number of Sites

This study will be conducted at 8-12 sites in the United States.

## 6.6 Number of Subjects

Anticipated accrual is 50 patients who receive at least one dose of RGI-2001, with at least 6 subjects in the Safety Run-in Phase, and up to 44 subjects in the Expansion Phase. It is anticipated that a minimum of 250 subjects will be included in the control group.

## 6.7 Study Duration

Individual subject participation is expected to last up to one year following alloHSCT, including a 6-week treatment period and a 42-week follow-up period. In addition, there is a screening period lasting approximately 2 weeks.

## 7 SUBJECT POPULATION

### 7.1 Inclusion Criteria

All subjects (including CIBMTR control group, except where noted) must meet the following criteria:

1. Ages  $> 18$  and  $\leq 65$  years of age
2. Has a hematologic malignancy as defined below and is considered a candidate for allo HSCT:
  - a. Acute myelogenous leukemia (AML) in first or subsequent morphologic complete remission
  - b. T or B cell acute lymphoblastic leukemia (ALL) in first or subsequent complete morphologic remission
  - c. Myelodysplastic syndrome (MDS), chronic myelomonocytic leukemia (CMML), myeloproliferative disorder (MPD) including myeloid metaplasia and myelofibrosis and are currently with  $< 10\%$  blasts in bone marrow
  - d. CML subjects who have received prior treatment including at least one tyrosine kinase inhibitor and are currently in chronic phase or with a complete hematologic remission but with evidence of cytogenetic or molecular relapse
3. Must have adequate organ function as defined below (RGI-2001 treatment group only):
  - a. Cardiac function: Left ventricular ejection fraction at rest  $\geq 45\%$
  - b. Liver function: total bilirubin  $< 1.5$  x upper limit of normal (ULN); alanine aminotransferase (ALT) and aspartate aminotransferase (AST)  $< 2.5$  x the ULN. Patients who have been diagnosed with Gilbert's Disease or malignant involvement are allowed to exceed the defined bilirubin value of  $1.5$  x the ULN
  - c. Serum creatinine  $< 2$  mg/dL or estimated creatinine clearance  $> 50$  mL/min calculated using the Cockcroft-Gault equation
  - d. Pulmonary: DLCO (corrected for hemoglobin) and/or FEV1  $\geq 50\%$
4. Considered suitable candidate for a myeloablative allogeneic or unrelated donor transplant based on institutional criteria
5. Subject must be receiving first allogeneic transplant from a single donor. Prior autologous transplant is acceptable
6. Transplant Donor:
  - a. Matched related donor (8/8): Molecular identity at HLA-A, -B, -C and -DRB1 by high-resolution typing
  - b. Unrelated donor ( $\geq 7/8$  allelic match): high resolution molecular typing at the following loci is required HLA -A, -B, -C and -DRB1
  - c. Meets institutional criteria for bone marrow or PBSC donation (see [Section 7.4](#))

7. Source of the Allograft:
  - a. Unmodified bone marrow or mobilized peripheral blood stem cell (PBSC) transplant, using granulocyte colony stimulating factor (G-CSF) as the mobilizing agent. Cord blood is not allowed
8. KPS  $\geq$  60
9. Is a candidate for anti-graft-vs-host-disease (GvHD) prophylaxis that includes:
  - a. A calcineurin inhibitor (either tacrolimus [FK 506] or cyclosporine A), in combination with either methotrexate (MTX), mycophenolate mofetil (MMF)
10. Ability to understand and willingness to sign a written informed consent form

Inclusion criteria pertaining specifically for subjects scheduled to receive RGI-2001:

11. If female of childbearing potential, must have had a negative serum pregnancy test prior to enrollment and must have agreed to use a double barrier method of contraception for 90 days following the last dose of RGI-2001
12. If male, must be sterile or willing to use an approved method of contraception from the time of informed consent to 90 days after the last dose of RGI-2001

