
 
• To assess the potential efficacy of RGI-2001 in addition to SOC vs SOC for the prevention of chronic GvHD (cGvHD) according to the secondary endpoints listed
 
• To assess the survival of subjects who received RGI-2001 in addition to SOC vs SOC
 
• To evaluate the pharmacodynamics (PD) effects of weekly dosing of RGI-2001
 
	
 
• Grades II-IV aGvHD by Day 180 according to the Modified Keystone Criteria
 
• Total and moderate-severe cGvHD at 6 months and 1 year according to the 2014 NIH criteria for cGvHD
 
• Non-relapse mortality (NRM) rates at Day 100, 6 months and 1 year
 
• Disease-free survival (DFS) at 6 months and 1 year
 
• GvHD-free, relapse free survival (GRFS) at 6 months and 1 year
 
• Overall survival (OS) at 6 months and 1 year
 
• Change from baseline in the percentage of CD4+CD25+CD45RA+ CD127-LO T cells (naive Tregs) on Days 14, 28, 42, 60, 100, 180
 

[REDACTED]
	
[REDACTED]

Study Design
	
This is an open-label, multi-center, single-arm study to evaluate six weekly doses of RGI-2001 in combination with SOC treatment for the prevention of aGvHD in subjects following alloHSCT. Study subjects will be compared to a contemporaneous set of controls from the Center for International Bone and Marrow Transplant Research (CIBMTR) that is derived using the same eligibility criteria

used for this study. The study will include a Safety Run-in Phase and an Expansion Phase.

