## 7.2 Exclusion Criteria

Any subjects (including CIBMTR control group) who meet any of the following criteria will be excluded from study entry:

1. Has had any other prior organ transplantation
2. Planned procedure to deplete regulatory T-cells from donor transplant materials
3. Planned reduced intensity conditioning
4. Planned use of any additional or alternative drug(s) for GvHD prophylaxis than listed in the inclusion criteria (e.g., rapamycin, cyclophosphamide, steroids)
5. Has had prior treatment with anti-CD3, other T cell depleting antibodies, or anti-thymocyte globulin within 12 months prior to alloHSCT procedure
6. Is participating in a trial (other than RGI-2001-003) involving an investigational agent/non-standard of care drug.
7. Has progressive underlying malignant disease including post-transplant lymphoproliferative disease.
8. Has evidence of active central nervous system (CNS) disease including known brain or leptomeningeal disease (CT or MRI scan of the brain required only in case of clinical suspicion of CNS involvement).
9. Known history of human immunodeficiency virus (HIV)
10. Active infection with hepatitis C virus (HCV) or hepatitis B virus (HBV) (control group only)

11. Is female and pregnant or lactating
12. Patients with active bacterial, viral or fungal infections (currently taking medication(s) and with progression or no clinical improvement)

Exclusion criteria pertaining specifically for subjects scheduled to receive RGI-2001:

13. Has undergone major surgery within 1 month before Day 0. Indwelling catheter placement is allowed
14. Hepatitis B virus (HBV) or hepatitis C virus (HCV) infection with viral load above the limit of quantification. Subjects that are on study with HBV or HCV infection should have titers checked regularly, as per institutional standard of care.
15. Has had any other condition that, in the opinion of the Investigator, renders the subject unsuitable for study participation
16. Has a documented history of uncontrolled autoimmune disease or on active treatment
17. Vaccinated with live, attenuated vaccines within 4 weeks of first dose of study drug.
18. History of myocardial infarction, unstable angina, or acute coronary syndrome within 6 months prior to receiving study drug
19. Has received an investigational agent within 4 half-lives or 14 days prior to HSCT, whichever is shorter

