### 12.3.1 Analysis of Efficacy Data

The primary endpoint grades II-IV acute GvHD by Day 100 according to the MAGIC criteria will be compared between the study group and CIBMTR controls using logistic regression. The factors that will be considered for adjustment in this model include subject age, gender, donor age, type of donor (MRD, 8/8 URD 7/8 URD), source of allograft, diagnosis (AML, ALL, MDS, MPD including CMML), preparative regimen, GvHD prophylaxis regimen.

Secondary endpoints that will be modeled as binary outcomes will similarly be compared using logistic regression. Secondary endpoints that will be modeled as time-to-event outcomes will be compared using Cox regression.

Potential interactions of RGI-2001 and various factors will be examined by including appropriate factors into regression models.

Given that this is not a randomized study and that the intention is only to assess outcomes for a potential signal, no adjustments will be made for multiple comparisons. As such, a Type II error (or a false negative) is prioritized over a Type I error (or a false positive).

Binary exploratory outcomes will be summarized with proportions, continuous outcomes with means and medians, and time-to-event outcomes with Kaplan-Meier estimates or cumulative incidence estimates for endpoints with competing risks.

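### Controls are exempt from the treated-only organ-function and exclusion criteria, contrary to the protocol's claims of equal eligibility, and the listed adjustment factors do not compensate, so NRM and OS are liable to bias towards RGI-2001

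*Protocol*

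**What the plan says.** **Who must meet what.** Protocol Section 7.1 opens its list with "All subjects (including CIBMTR control group, except where noted) must meet the following criteria". Inclusion 3, which sets cardiac, hepatic, renal and pulmonary limits, is one of the noted exceptions: "Must have adequate organ function as defined below (RGI-2001 treatment group only". Section 7.2 ends with a block headed "Exclusion criteria pertaining specifically for subjects scheduled to receive RGI-2001", items 13 to 19. Among these are item 18, "History of myocardial infarction, unstable angina, or acute coronary syndrome within 6 months prior to receiving study drug", and item 15, "Has had any other condition that, in the opinion of the Investigator, renders the subject unsuitable for study participation", together with recent major surgery and uncontrolled or actively treated autoimmune disease. The synopsis carries the same labels.

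**How the controls are described.** The synopsis (Study Design) refers to a contemporaneous control set "that is derived using the same eligibility criteria" as the trial. Section 6.3 states: "Control subjects will be chosen so as to meet all eligibility requirements for the clinical trial". The synopsis repeats this under Control Group and Statistical Considerations, and Section 12 repeats it in its first paragraph. Section 7.3 instead asks controls to satisfy the criteria as set out in Section 7.

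**Adjustment.** Section 12.3.1 and the synopsis list patient age, gender, donor age, donor type, and then "source of allograft, diagnosis (AML, ALL, MDS, MPD including CMML), preparative regimen, GvHD prophylaxis regimen". No separate list is given for the Cox models of the time-to-event secondary endpoints. SAP Sections 2.3 and 8.0 leave the registry comparison to a separate SAP.

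**The concern.** A patient at a participating centre who fails an organ-function limit, or has had a recent coronary event, cannot enter the RGI-2001 group but can still become a control. That selection favours the treated group on mortality before any drug is given. NRM, OS, DFS and GRFS are all secondary comparative endpoints, and a death can count in each of them.

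Two features make this matter more. The synopsis accepts a one-sided 0.10 level as a signal, with no multiplicity adjustment. And a reader who relies on Section 6.3 or Section 12 would believe that eligibility had been matched, and so would not look for a fitness difference when reading a favourable survival result.

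**Working it through.** **Step 1: set the texts side by side.**

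- Inclusion 3 and exclusions 13–19 do not bind controls. The statements that controls share the same criteria (synopsis, Study Design) or meet every requirement (synopsis, Control Group and Statistical Considerations; Sections 6.3 and 12) therefore cannot be literally true.
- Section 7.3 does not conflict. It points to Section 7, which contains the exemptions.
- Not every treated-only item concerns fitness. Items 17 (live vaccine) and 19 (recent investigational agent) are not obviously prognostic. Item 14 (hepatitis B or C viral load) is roughly offset by the control-only exclusion of active hepatitis. The prognostic weight lies in inclusion 3 and items 13, 15, 16 and 18.
- No control-only criterion works in the opposite direction on organ function or cardiac history.

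**Step 2: illustrate the size.** The plan gives no figure to reproduce; the rates behind the sample size are blacked out. The inputs are:

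- 50 treated and 250 controls (Section 6.6); one-sided 0.10 (synopsis).
- Base NRM of 10% in subjects who meet the limits. This is an assumption. It borrows the Day-100 level that Section 12.4 calls excessive, which is a safety threshold and not an expected control rate.
- s, the share of controls outside the treated-only limits, and RR, their NRM relative to other controls. Both are assumptions; the documents give neither.
- No drug effect.

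Control NRM = 10% × (1 − s + s × RR). Apparent relative reduction = 1 − 10% / control NRM.

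For example, s = 30% and RR = 2.0 give 10% × (0.7 + 0.6) = 13.0%, and 1 − 10/13 = 23.1%.

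The last column is the chance of a favourable one-sided p < 0.10 from an unadjusted pooled z-test, by exact enumeration of the two binomials.

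| s | RR | Control NRM | Gap (points) | Apparent relative reduction | P(favourable p < 0.10) |
|---|---|---|---|---|---|
| 0 | – | 10.0% | 0 | 0 | 0.099 |
| 5% | 1.5 | 10.25% | 0.25 | 2.4% | 0.108 |
| 10% | 1.5 | 10.5% | 0.5 | 4.8% | 0.117 |
| 10% | 2.0 | 11.0% | 1.0 | 9.1% | 0.137 |
| 20% | 1.5 | 11.0% | 1.0 | 9.1% | 0.137 |
| 20% | 2.0 | 12.0% | 2.0 | 16.7% | 0.181 |
| 30% | 1.5 | 11.5% | 1.5 | 13.0% | 0.158 |
| 30% | 2.0 | 13.0% | 3.0 | 23.1% | 0.233 |

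The apparent relative reduction does not depend on the base rate, because the base cancels. The false-signal rate does: at s = 20% and RR = 2.0 it is 0.147 from a 5% base and 0.248 from a 20% base.

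**Step 3: room for extra covariates.** At 10% NRM, 300 subjects yield about 30 Day-100 events. Treatment (1), age (1), gender (1), donor age (1), donor type (2), graft source (1), diagnosis (3), preparative regimen (at least 1) and prophylaxis (at least 1) already use about 12 parameters, or 30/12 = 2.5 events each.

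**The case against.** **The controls are not unselected.** Age up to 65, Karnofsky of at least 60, institutional suitability for a myeloablative transplant, no planned reduced-intensity conditioning, no progressive malignancy, no uncontrolled infection and no HIV apply to both groups, and controls come from the same centres and time window. This stands, and it narrows the gap. It does not close it. Karnofsky 60 is a floor that admits everything from 60 to 100, and the protocol still saw reason to add organ-function limits for treated subjects.

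**The final model has not been seen.** A reader might infer that the comparison will contain no fitness variable. The documents do not show that. Section 12.3.1 presents its list as factors under consideration and as including those named, parts of the statistics text are blacked out, and the comparison SAP is a separate document. What can be said is that the only prespecification available names none.

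**Remission status is a different matter.** Its absence does not arise from the exemption, since the remission and blast-count requirements apply to both groups. It is a general prognostic confounder and should be argued as such: first or subsequent remission covers a wide range of risk.

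**The comparison is openly non-randomised and signal-seeking.** True, and the exemptions themselves are plainly labelled. That does not excuse statements of equal eligibility which the criteria contradict.

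**Conclusion.** The contradiction in the eligibility statements is certain and needs correcting whatever the comparison SAP says. The listed factors do not offset the difference in selection, so NRM and OS are liable to bias towards RGI-2001. DFS and GRFS are affected less, because relapse (SAP Section 8.4) and GvHD events (SAP Section 8.7) dilute the mortality component. No size was calculated for OS, DFS or GRFS.

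A stronger reading, that these endpoints are shown to be biased, is not supported. The direction is expected whenever some controls fall outside the limits and carry excess risk, but neither quantity is documented. Under the illustrative assumptions the spurious NRM gap is 0.5 to 3.0 points, an apparent relative reduction of about 5–23%. At s = 5% and RR = 1.5 it is negligible. For scale, 50 against 250 at one-sided 0.10 has 80% power for a reduction of about 8 points from 10%. The point does not extend to the primary endpoint, for which no effect was derived.

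**What to change.** 1. **Wording.** In the synopsis (Study Design, Control Group, Statistical Considerations) and in Sections 6.3 and 12, state that controls meet the criteria not marked as applying to the RGI-2001 group only. Section 7.3 can stay.
2. **Adjustment.** Add Karnofsky score to the prespecified factors in the protocol and in the comparison SAP. Add remission or disease status at transplant as well, justified separately as a prognostic confounder. Include comorbidity or organ function where the comprehensive registry forms hold it. Karnofsky and remission status are eligibility items for both groups, so they should already be known; Section 11.2 places controls on the comprehensive reporting track. Because NRM events are few, use a parsimonious model or a propensity score rather than adding every term to each regression.
3. **Sensitivity analysis.** Repeat the NRM, OS, DFS and GRFS comparisons with controls restricted to those who meet the treated-only criteria that can be checked in registry data, and report how many are removed. That count estimates s directly. Investigator-judged unsuitability cannot be checked this way and should be named as a residual limitation.

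The cost is a wording change in two documents, a few degrees of freedom, and one additional run with somewhat fewer controls.
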